9.3 Health economic analyses

Health economic analysis will include two components:

1. A within trial analysis will profile the short-term patterns of health and social care resource utilisation and health impacts over the observable 24-month trial period, and examine relative short term cost-efficiency of each trial.
2. A long run cost-efficiency model, extrapolating changes patient outcomes over a lifetime horizon to account for future impacts on the need for TKR and associated revision, and their timing relative to retirement.

Full details of these analyses will be specified in a comprehensive Health Economic Analysis Plan, authored by the study health economist(s), and signed off by the PI prior to analysis, however the following section offers an overview:

To maximise UK policy relevance, health economic analysis will follow NICE reference case recommendations (53) including: The adoption of an NHS and PSS (personal social service) costing perspective for primary analyses; cost-utility approach (results presented in terms of incremental cost effectiveness ratios (ICERs) on a cost per quality adjusted life year (QALY) basis, with QALYs derived from EQ-5D-5L utility scores using NICE's preferred scoring algorithm at time of analysis); choice of discount rate (where applicable); and use of probabilistic sensitivity analysis (PSA). Secondary analysis will investigate the impact of treatment choice on employment status.

Several key items of health care resource utilisation (HCRU) for the first 24 months post randomisation will be collected retrospectively from medical records, namely: Inpatient admissions; A&E visits; ambulance trips; physiotherapy, and other outpatient visits. Additional top up self-report surveying will be undertaken alongside EQ-5D-5L and other PROMs at 12 and 24 months for: primary care, pain medications; employment status; and any HCRU not obtainable from medical records. HCRU will be combined with standard UK price weights (54) to estimate costs with a base year set to the latest financial year for which at least one study participant provides data.

The within trial analysis (component 1) will describe rates of resource use, associated cost, and health utility scores/QALYs, will be presented contextually as summary statistics for each trial arm, with comparisons of total cost and QALYs undertaken Generalised Linear Modelling to account for anticipated skew (55) Incremental cost per QALY will be estimated by appropriate technique with preference given a recycled predictions approach (56) if data permits. The proportion of patients changing employment status will be examined using logistic regression.

Missing data will be imputed using appropriate techniques depending on degree of missingness, most likely multiple imputation by chained equations (which is considered gold standard in this area (57)). It is however worth noting that the most important cost factors relate to inpatient readmission and outpatient activity, will be obtained from medical records thus are not anticipated be prone to missingness.

Longer run cost-efficiency in terms of incremental cost per QALY will be examined by means of decision analytic simulation modelling (Component 2), This will extrapolate patient outcomes over a lifetime horizon to account for future impacts on the need for TKR and associated revision, and their timing relative to retirement since these often have significant impacts on employment potential and related. Initial scoping suggests this to be at least achievable Markov modelling, though as available data appear to be rich, more sophisticated options will be explored as needed. Initially reporting from the model will utilise the 24-month trial data, complimented with NJR and KOR data on longer term rates of TKR, revision TKR, and associated EQ-5D utility scores, a recent Cochrane review (12), topped up to date of analysis, and parameters extracted from a similar model (58). Additional, potentially non-systematic, targeted literature searches may be necessary for specific parameters if not available from these sources.

Uncertainty around both within trial and modelled ICERs will be presented using PSA with cost-effectiveness acceptability curves (CEAC) generated. Should the model prove inconclusive, value of information analysis will be undertaken to identify critical parameters which are driving overall uncertainty in decision criteria to inform follow up research potentially using the data linkage permissions obtained at consent.

9.4 Process Evaluation

In line with MRC guidance (52) a mixed method process evaluation will be conducted. The overall aim is to assess the acceptability and feasibility of the intervention from staff and patients. Specifically, it will address the following research objectives: (a) explore trial eligibility, recruitment and retention rates (b) acceptability of intervention implementation including trial processes and the collection of routine monitoring data (c) patient experience of taking part and the contextual factors that influence this.

A. Process evaluation design and sample: The design will comprise of two parts. Part 1 will be embedded within the pilot study, providing delivery detail and context to

support the main trial. Data will be collected, via semi-structured telephone/video interviews from delivery staff (n=12, surgeons/physiotherapists/research nurses) at three sites and patients enrolled in the pilot stage (n=15- 20, minimum of four from each site and minimum of four from the control arm) to capture initial understanding/expectations of the trial. They will then be followed up once (via semi-structured telephone interview) during the pilot study (months 3-6). Staff interviews will explore experiences of taking part, challenges to recruitment/implementation and issues related to trial delivery. Patient interviews will explore willingness to be randomised and acceptability of intervention or the non-surgical package if in comparison group. Findings will be fed back to the Trial Management Group and Trial Steering Committee to improve recruitment/trial delivery for the definitive trial. Part 2 will extend the process evaluation into the definitive trial. This is important because the pilot trial data captures just one follow-up from three sites, providing limited detail on the research objectives listed above and the factors that influence this. By extending the process evaluation into the definitive trial, the design will move to a prospective, longitudinal, cohort study across six sites. The total sample will be boosted to 20 staff and 30-40 patients (~7-10 control and ~23-30 intervention, spread across the three sites). This will further our understanding of the trial implementation, context (delivery may vary by site, for example) and the mechanisms that influence delivery. It will also provide a richer narrative of the patient journey and stakeholder views, which will inform future roll out and create transferable learning to other disciplines. For example, a key area is to explore movement from the non-surgical to surgical arm of the trial. Being able to examine this over multiple time periods will generate a greater depth of understanding of the context in which this occurs and the factors that influence the patient decision to switch. Patients will receive three further telephone interviews. The first at six months and then at 12 and 24 months in line with the clinical follow up. To prevent sample attrition, patients will receive £15 for each completed interview. Finally, it is important to understand the reasons why potentially eligible patients decided not to take part in the trial and if there is anything that could have been done differently to encourage participation in the future. We will, therefore, conduct 10 telephone interviews with these patients, who will also be given a £25 voucher.

B. Recruitment and analysis: Recruitment of patients will be guided by a purposive sampling frame to ensure diversity of key characteristics e.g. trial site, treatment arm, age, gender, urban rural residence. Interviews will be digitally recorded and transcribed verbatim by an in house employee of the University of Edinburgh. Audio files will be saved within the secure project folder prior to being downloaded for transcription. Once the transcript is checked, the audio file will be deleted.

We will use a thematic approach to analyse the data, facilitated by NVivo 12. First, we will read the transcripts to identify the key topics and issues which emerge from data. Next, a draft analytical framework will be created, piloted, refined and finalised by the project team. Each transcript will then be coded and summarised into key themes using Framework matrices, or charts. This approach reduces large volumes of data and facilitates systematic between and within case analysis. It also allows for emergent patterns and explanations to be explored and tested and, thus, provides the depth required to move beyond description and into interpretative analysis, which is the aim of qualitative analysis. The use of NVivo 12 ensures that analysis is fully documented and conclusions can be clearly linked back to the original source data.

10 ADVERSE EVENTS

Adverse events will be collected throughout the trial. Events related to a worsening of co-morbid conditions known at time of randomisation and any events related to the known risk associated with surgery will not be reported as adverse events. Complications already covered under secondary outcomes (Protocol Section 2.2) will not be recorded as adverse outcomes. Adverse events will be collected for all patients up to their final (24-month) follow up. These do not require to be reported to the Sponsor.

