1.2.2 Comparator – Non-surgical treatment (Personalised Knee Therapy, PKT)

A. Rationale: The MOTION non-surgical intervention is a specialised package of knee rehabilitation and represents physiotherapist-led best-care for medial compartment knee OA. It is based on best-practice guidance and was developed with a team of physiotherapy academics from Edinburgh Napier University and clinical specialist physiotherapists from NHS Lothian following an evidence review and with considerable PPI involvement throughout. Our PPI group reviewed the proposed rehabilitation package and considered it to be very different from the physiotherapy they may have received in the community before referral to secondary care. This package of 'Personalised Knee Therapy' (PKT) has also been 'road-tested' at the lead site by the co-applicant (DH) as part of the development of the MOTION trial drawing on the experience of delivering non-operative interventions in multi-site clinical trials in the UK (32,35). Patients were particularly keen to ensure a comprehensive non-operative intervention that is distinct from any previous therapy they may have received earlier in the disease process (prior to referral to secondary care). A core package will deliver (a) progressive structured exercise programme (b) advice on lifestyle, pain management and (where appropriate) weight management. There will be an optional inclusion of biomechanical interventions (bracing or insoles), manual therapy, steroid injection and treatment of additional co-existing symptoms (that interact with and exacerbate the knee symptoms) where this falls within local usual care. The intervention will be delivered over 6 outpatient contact sessions with a specialist physiotherapist over a period not exceeding 4 months.

B. Risks: The risks with non-surgical intervention are much less compared to the surgical intervention but include pain exacerbation from exercise therapy, steroid induced pain exacerbation or joint infection and skin breakdown from brace/orthotic usage.

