2.2 ENDPOINTS

The primary and secondary endpoints will be captured within the following framework: **Population** - NHS patients <60 years with symptomatic knee OA localised to the medial compartment in whom surgical intervention is indicated. **Intervention** - Surgery with medial opening wedge HTO followed by standard postoperative rehabilitation based on local pathways. **Comparator** - Non-surgical intervention with Personalised Knee Therapy (PKT) delivered within an NHS physiotherapy department.

Primary endpoint

The primary outcome is the composite 24-month Knee Injury and Osteoarthritis Outcome Score (KOOS) score (www.koos.nu).

Secondary endpoints

1. Minimum requirements/acceptable variation (MRAV) proforma completed between 6 -12 months post intervention (note that this interval may be different from the same period post-randomisation due to NHS waiting lists)
2. KOOS composite score 12 months post-randomisation.
3. Five separate KOOS subscales at 12 and 24-months post randomisation.
4. Oxford Knee score (OKS, www.innovation.ox.ac.uk) at 12 and 24- months post-randomisation (46).
5. Forgotten Joint Score-12 (FJS-12, www.forgotten-joint-score.info) at 12 and 24-months post-randomisation (47,48).
6. EuroQol EQ-5D-5L score ([EQ-5D-5L – EQ-5D \(euroqol.org\)](http://EQ-5D-5L - EQ-5D (euroqol.org))) (49)
7. Pittsburgh Sleep Problem Scale at 12 and 24-months post randomisation (32)
8. Return to Work/Employment Questionnaire (9,10).

9. Additional study-knee related operative intervention at 12 and 24-months post randomisation

10. Intraoperative and postoperative complications 12 and 24 months post-randomisation

11. Health Economic Evaluation Outcomes

- a. Health and social care resource utilisation and associated NHS and PSS cost and Quality Adjusted life years (QALY) at 24 months
- b. Incremental Cost per QALY at 24 months
- c. NHS and PSS cost, and QALYs as modelled over a lifetime horizon to account for future impacts on the need for TKR and associated revision surgery and their timing relative to retirement
- d. Incremental Cost per QALY as modelled over a lifetime horizon to account for future impacts on the need for TKR and associated revision surgery and their timing relative to retirement.

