6 STUDY ASSESSMENTS

Participant Follow-up at 12 and 24 months

All available methods of communication will be used for the study assessments including email, post, telephone and NHS approved video links (e.g. NearMe), with a maximum of two reminders sent where required. The preferred method for collection of baseline data will be with a face-face consultation. Where local circumstances prevent this, baseline data may also be collected by telephone or video link. After collection of the baseline data, follow up will occur at two further intervals - 12 and 24 months post-randomisation, with all study assessments at these time points undertaken remotely via email, post or telephone.

Minimum requirements/acceptable variations (MRAV) proforma

A standardised minimum requirements/acceptable variations (MRAV) proforma will be completed for each participant approximately 6 months post intervention to record the fidelity of the trial interventions. This proforma will be completed by the local research team at each participating centre. It should be noted that this proforma is collected from approximately 6 months post-intervention, and this interval may be different from the time period since randomisation due to NHS waiting lists. In the Personalises Knee Therapy (PKT) group, data will be collected and recorded at each one-to-one session. The date of the last one-to-one physiotherapy session (usually the 6th session) will be considered as the date for completion of the intervention.

Table 2: Tabulated summary of assessments						
ASSESSMENT	Screening	Baseline	6-month MRAV proforma (HTO)	6-month MRAV proforma (PKT)	12-month PROMS	24-month PROMS
Who is responsible for assessment?	Local site team	Local site team	Local site team	Local site team	ECTU	ECTU
Allowed variation in months			±6	±6	±3	±3
How is assessment done?	Clinic review and/or Medical records review	Clinic review	Medical records review	Patient attendance at 6 supervised physiotherapy sessions Medical records review Patient exercise diary review	Email and/or Post and /or Online portal	Email and/or Post and /or Online portal
Assessment of eligibility criterion	X	X				
Log of eligible patients excluded (declined, exclusion criterion, other reason)		X				
Written Informed consent		X				
Baseline data & demographics		X				
Randomisation		X				
Minimum requirement/acceptable variation (MRAV) proforma			X	X		
Primary outcome score – KOOS		X			X	X

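### Adverse event reporting exempts known surgical risks but not known physiotherapy risks, and remote follow-up is the only scheduled source for complications

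*Protocol*

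**What the plan says.** Protocol section 10 collects adverse events throughout the trial: "Adverse events will be collected for all patients up to their final (24-month) follow up". It then makes exemptions. Worsening of co-morbidities known at randomisation is exempt in both arms. In addition, "any events related to the known risk associated with surgery will not be reported as adverse events". Finally, "Complications already covered under secondary outcomes (Protocol Section 2.2) will not be recorded as adverse outcomes".

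Section 1.2.1 lists the known surgical risks, among them infection, thromboembolism, intra-operative fracture, non-union and under- or overcorrection. Section 1.2.2 lists the known risks of the comparator, which "include pain exacerbation from exercise therapy, steroid induced pain exacerbation or joint infection and skin breakdown from brace/orthotic usage". Section 10 does not exempt these.

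The outcomes that take over the surgical harms are in section 2.2. Endpoint 9 is "Additional study-knee related operative intervention at 12 and 24-months post randomisation" and endpoint 10 is "Intraoperative and postoperative complications 12 and 24 months post-randomisation".

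Table 2 marks both outcomes only in the 12- and 24-month columns. These are the responsibility of the trials unit, and section 6 describes them "with all study assessments at these time points undertaken remotely via email, post or telephone". The columns for the minimum requirements/acceptable variation (MRAV) proforma, completed by sites with medical records review in both arms, carry no mark for complications. Table 2 has no row for adverse events. Section 9.3 plans a further records source: several items of resource use "will be collected retrospectively from medical records" over 24 months, including admissions, emergency visits and outpatient visits.

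**The concern.** Two separate problems arise.

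First, the adverse event rule is one-sided. Joint infection after a steroid injection given within PKT is reportable as an adverse event; infection after HTO is a known surgical risk and is not. A table of adverse events by arm would then reflect the reporting rule as well as the treatments, and the distortion favours surgery.

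Second, the endpoint that receives the surgical harms has only remote patient follow-up as its scheduled source. A patient may not know of an intra-operative fracture or of under- or overcorrection. These are the events that the exemption sends to endpoint 10.

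At stake are a named secondary endpoint and the safety comparison in a trial of surgery against no surgery.

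**Working it through.** **The rule, arm by arm**

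| Event type | Adverse event count | Other stated home | Scheduled source for that home |
|---|---|---|---|
| Known surgical risk | Exempt (section 10) | Endpoint 10; endpoint 9 if it leads to a further knee operation | Remote contact at 12 and 24 months (Table 2) |
| Known PKT risk | Included | None needed | – |

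The exemption is worded by procedure, not by arm, so it also covers PKT patients who cross over to surgery. Under the 20% crossover assumed in section 9.1, that is 0.20 × 112 = 22.4 patients. The asymmetry between randomised arms is reduced but not removed.

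**Inputs**

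- Arm size: 112 (section 9.1).
- Rate of major complications and severe adverse events after HTO: 5% to 10% (section 1.2.1).
- Share of complications captured by remote follow-up: not given, so treated as an assumption.

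**Arm size.** The protocol uses a difference of 7.2, SDs of 14.4 and 15.9, two-sided 0.05 and 90% power. The normal approximation gives (1.960 + 1.282)² × (14.4² + 15.9²) / 7.2² = 93.3, so 94 per group. The noncentral t gives 95 (power 0.902 at 95 and 0.899 at 94), which is the protocol's figure. With 15% loss, 95 / 0.85 = 111.8, so 112. The arm size is reproduced.

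**Expected surgical events, if all 112 receive HTO**

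- At 5%: 112 × 0.05 = 5.6. Chance of at least one: 1 − 0.95^112 = 0.997.
- At 10%: 112 × 0.10 = 11.2. Chance of at least one: above 0.9999.

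The same rates in 22.4 crossover patients give 1.1 to 2.2 further exempted events in the PKT arm.

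**Events seen in endpoint 10, by assumed capture**

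| Assumed capture | At 5% | At 10% |
|---|---|---|
| 100% | 5.6 | 11.2 |
| 85% | 4.8 | 9.5 |
| 70% | 3.9 | 7.8 |
| 50% | 2.8 | 5.6 |

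The first row shows events classed under another heading, with none lost. The other rows show what incomplete capture would cost. The documents do not say which row applies. They also give no rate for the PKT risks, so a net difference between arms cannot be calculated.

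**The case against.** A reader might infer that harms overall will be under-counted in the surgical arm, and that any risk–benefit statement about HTO will be biased in its favour. The documents do not support that reading.

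- Section 10 moves surgical harms to pre-specified secondary endpoints. The 6 to 11 events are reclassified, not lost. This stands.
- Adverse event counts are not an endpoint, and section 9.2 plans no between-arm comparison of them. Tabulation is left to a separate analysis plan that was not available. This stands in part: the one-sided rule misleads only if adverse events are shown without the complications. But nothing in the protocol requires the two to be shown together.
- The source of complications data is not restricted to patient recall. Section 7.1 says source documents are detailed elsewhere, and nothing excludes site records. Sites review HTO patients' records for the MRAV proforma, and section 9.3 takes admissions and outpatient visits from records, so harms leading to readmission leave a trace. This stands, and it makes under-ascertainment a risk only. It does not close the gap. The stated purpose of the MRAV proforma is fidelity, the section 9.3 extraction counts resource use rather than complications, and a fracture during the index operation need not create a separate item.
- The event figure assumes that every patient allocated to HTO receives it and that every event is an exempted risk. This stands; it is an illustration.

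An analysis plan could combine the two kinds of event. It could not supply events that were never collected.

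**Conclusion.** The point holds in two parts of different strength. It is certain from the text that known surgical risks are outside the adverse event count while known PKT risks are inside it. Adverse event counts alone are therefore not comparable between arms and will favour surgery. At the protocol's rates this concerns about 6 to 11 events among 112 HTO patients, provided all have surgery and the events are known surgical risks.

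It is a risk, not an established fact, that endpoint 10 will miss surgical complications. Its only scheduled source is remote follow-up, and the documents give no capture rate.

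This should be fixed. It does not touch the primary endpoint, sample size, power or primary analysis.

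**What to change.** 1. In section 10, either apply one harm definition to both arms, or state that adverse events and complications will be reported together by randomised arm and seriousness. The second option makes deletion of the surgical exemption unnecessary. In a combined table, count each participant once per category, so that an event recorded under more than one heading is not counted twice.
2. In Table 2, name site medical records as the source for complications and additional knee operations in both arms, with patient report as a supplement. Use both the MRAV review and the records extraction planned in section 9.3. The MRAV review is timed about 6 months after the intervention, so it does not by itself cover the period to 24 months after randomisation.
3. Add an adverse event row to Table 2, so that the schedule matches the collection that section 10 promises.

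The cost is a protocol amendment, a few extra electronic case report form fields within record reviews already planned, and slightly more recording work at sites. No sample size or power figure changes.
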